5.5 Concomitant Medications/Vaccinations (allowed & prohibited)

Medications or vaccinations specifically prohibited in the exclusion criteria are not allowed during the ongoing trial. If there is a clinical indication for one of these or other medications or vaccinations specifically prohibited during the trial, discontinuation from trial therapy or vaccination may be required. The investigator should discuss any questions regarding this with the study PI or co-PI. The final decision on any supportive therapy or vaccination rests with the investigator and/or the subject's primary physician.

5.5.1 Acceptable Concomitant Medications

All treatments that the investigator considers necessary for a subject's welfare may be administered at the discretion of the investigator in keeping with the community standards of medical care. All concomitant medication will be recorded on the case report form (CRF) including all prescription, over-the-counter (OTC), herbal supplements, and IV medications and fluids. If changes occur during the trial period, documentation of drug dosage, frequency, route, and date may also be included on the CRF.

All concomitant medications received within 28 days before the first dose of trial treatment and during trial treatment should be recorded.

See Section 5.2.2.1. for more detailed information on concomitant medications specifically during the hospitalization for IL-2 therapy.

5.5.2 Prohibited Concomitant Medications

Subjects are prohibited from receiving the following therapies during the Screening and Treatment Phase (including retreatment for post-complete response relapse) of this trial:

- Antineoplastic systemic chemotherapy or biological therapy other than pembrolizumab and IL-2
- Immunotherapy not specified in this protocol
- Chemotherapy not specified in this protocol
- Investigational agents
- Radiation therapy
 - Note: Radiation therapy to a symptomatic solitary lesion or to the brain may be allowed at the investigator's discretion.
- Live vaccines within 30 days prior to the first dose of trial treatment and while participating in the trial. Examples of live vaccines include, but are not limited to, the following: measles, mumps, rubella, varicella/zoster, yellow fever, rabies, BCG, and typhoid vaccine.
- Systemic glucocorticoids for any purpose other than to modulate symptoms from an event of clinical interest of suspected immunologic etiology. The use of physiologic doses of corticosteroids may be approved after consultation with the study PI or co-PI.

Subjects who, in the assessment by the investigator, require the use of any of the aforementioned treatments for clinical management should be removed from the trial. Subjects may receive other medications that the investigator deems to be medically necessary.

The Exclusion Criteria describes other medications which are prohibited in this trial.

There are no prohibited therapies during the Post-Treatment Follow-up Phase.

5.6 Rescue Medications & Supportive Care

5.6.1 Supportive Care Guidelines

Subjects should receive appropriate supportive care measures as deemed necessary by the treating investigator. Suggested supportive care measures for the management of adverse events with potential immunologic etiology are outlined below and in greater detail in the ECI guidance document. Where appropriate, these guidelines include the use of oral or intravenous

treatment with corticosteroids as well as additional anti-inflammatory agents (i.e. infliximab) if symptoms do not improve with administration of corticosteroids. Note that several courses of steroid tapering may be necessary as symptoms may worsen when the steroid dose is decreased. For each disorder, attempts should be made to rule out other causes such as metastatic disease or bacterial or viral infection, which might require additional supportive care. The treatment guidelines are intended to be applied when the investigator determines the events to be related to pembrolizumab.

Note: if after the evaluation the event is determined not to be related, the investigator is instructed to follow the ECI reporting guidance but does not need to follow the treatment guidance (as outlined in the ECI guidance document). Refer to Section 5.4 for dose modification.

It may be necessary to perform conditional procedures such as bronchoscopy, endoscopy, or skin photography as part of evaluation of the event. Suggested conditional procedures, as appropriate, can be found in the ECI guidance document.

- **Pneumonitis:**

- For **Grade 2 events**, treat with systemic corticosteroids. When symptoms improve to Grade 1 or less, steroid taper should be started and continued over no less than 4 weeks.
- For **Grade 3-4 events**, immediately treat with intravenous steroids. Administer additional anti-inflammatory measures, as needed.
- Add prophylactic antibiotics for opportunistic infections in the case of prolonged steroid administration.

- **Diarrhea/Colitis:**

Subjects should be carefully monitored for signs and symptoms of enterocolitis (such as diarrhea, abdominal pain, blood or mucus in stool, with or without fever) and of bowel perforation (such as peritoneal signs and ileus).

- All subjects who experience diarrhea/colitis should be advised to drink liberal quantities of clear fluids. If sufficient oral fluid intake is not feasible, fluid and electrolytes should be substituted via IV infusion. For Grade 2 or higher diarrhea, consider GI consultation and endoscopy to confirm or rule out colitis.
- For **Grade 2 diarrhea/colitis** that persists greater than 3 days, administer oral corticosteroids.
- For **Grade 3 or 4 diarrhea/colitis** that persists > 1 week, treat with intravenous steroids followed by high dose oral steroids.
- When symptoms improve to Grade 1 or less, steroid taper should be started and continued over no less than 4 weeks.

- **Type 1 diabetes mellitus (if new onset, including diabetic ketoacidosis [DKA]) or \geq Grade 3 Hyperglycemia, if associated with ketosis (ketonuria) or metabolic acidosis (DKA)**
 - For **T1DM or Grade 3-4 Hyperglycemia**
 - Insulin replacement therapy is recommended for Type I diabetes mellitus and for Grade 3-4 hyperglycemia associated with metabolic acidosis or ketonuria.
 - Evaluate patients with serum glucose and a metabolic panel, urine ketones, glycosylated hemoglobin, and C-peptide.

- **Hypophysitis:**
 - For **Grade 2** events, treat with corticosteroids. When symptoms improve to Grade 1 or less, steroid taper should be started and continued over no less than 4 weeks. Replacement of appropriate hormones may be required as the steroid dose is tapered.
 - For **Grade 3-4** events, treat with an initial dose of IV corticosteroids followed by oral corticosteroids. When symptoms improve to Grade 1 or less, steroid taper should be started and continued over no less than 4 weeks. Replacement of appropriate hormones may be required as the steroid dose is tapered.

- **Hyperthyroidism or Hypothyroidism:**

Thyroid disorders can occur at any time during treatment. Monitor patients for changes in thyroid function (at the start of treatment, periodically during treatment, and as indicated based on clinical evaluation) and for clinical signs and symptoms of thyroid disorders.

 - **Grade 2 hyperthyroidism events (and Grade 2-4 hypothyroidism):**
 - In hyperthyroidism, non-selective beta-blockers (e.g. propranolol) are suggested as initial therapy.
 - In hypothyroidism, thyroid hormone replacement therapy, with levothyroxine or liothyronine, is indicated per standard of care.
 - **Grade 3-4 hyperthyroidism**
 - Treat with an initial dose of IV corticosteroid followed by oral corticosteroids. When symptoms improve to Grade 1 or less, steroid taper should be started and continued over no less than 4 weeks. Replacement of appropriate hormones may be required as the steroid dose is tapered.

- **Hepatic:**
 - For **Grade 2** events, monitor liver function tests more frequently until returned to baseline values (consider weekly).
 - Treat with IV or oral corticosteroids
 - For **Grade 3-4** events, treat with intravenous corticosteroids for 24 to 48 hours

- When symptoms improve to Grade 1 or less, a steroid taper should be started and continued over no less than 4 weeks.
- **Renal Failure or Nephritis:**
 - For **Grade 2** events, treat with corticosteroids.
 - For **Grade 3-4** events, treat with systemic corticosteroids.
 - When symptoms improve to Grade 1 or less, steroid taper should be started and continued over no less than 4 weeks.

Management of Infusion Reactions: Signs and symptoms usually develop during or shortly after drug infusion and generally resolve completely within 24 hours of completion of infusion.

Table 5 below shows treatment guidelines for subjects who experience an infusion reaction associated with administration of pembrolizumab.

Table 5 Infusion Reaction Treatment Guidelines

NCI CTCAE Grade	Treatment	Premedication at subsequent dosing
Grade 1 Mild reaction; infusion interruption not indicated; intervention not indicated	Increase monitoring of vital signs as medically indicated until the subject is deemed medically stable in the opinion of the investigator.	None
Grade 2 Requires infusion interruption but responds promptly to symptomatic treatment (e.g., antihistamines, NSAIDS, narcotics, IV fluids); prophylactic medications indicated for <=24 hrs	
Stop Infusion and monitor symptoms. Additional appropriate medical therapy may include but is not limited to:
 
 IV fluids Antihistamines NSAIDS Acetaminophen Narcotics 
Increase monitoring of vital signs as medically indicated until the subject is deemed medically stable in the opinion of the investigator. If symptoms resolve within one hour of stopping drug infusion, the infusion may be restarted at 50% of the original infusion rate (e.g., from 100 mL/hr to 50 mL/hr). Otherwise dosing will be held until symptoms resolve and the subject should be premedicated for the next scheduled dose.
 
Subjects who develop Grade 2 toxicity despite adequate premedication should be permanently discontinued from further trial treatment administration.
	
Subject may be premedicated 1.5h (± 30 minutes) prior to infusion of pembrolizumab (MK-3475) with:
 
Diphenhydramine 50 mg po (or equivalent dose of antihistamine).
 
Acetaminophen 500-1000 mg po (or equivalent dose of antipyretic).

Grades 3 or 4 Grade 3: Prolonged (i.e., not rapidly responsive to symptomatic medication and/or brief interruption of infusion);	
Stop Infusion. Additional appropriate medical therapy may include but is not limited to:
 
 IV fluids Antihistamines NSAIDS 	No subsequent dosing

NCI CTCAE Grade	Treatment	Premedication at subsequent dosing

recurrence of symptoms following initial improvement; hospitalization indicated for other clinical sequelae (e.g., renal impairment, pulmonary infiltrates)
 
Grade 4: Life-threatening; pressor or ventilatory support indicated
	
Acetaminophen Narcotics Oxygen Pressors Corticosteroids Epinephrine
 
Increase monitoring of vital signs as medically indicated until the subject is deemed medically stable in the opinion of the investigator. Hospitalization may be indicated. Subject is permanently discontinued from further trial treatment administration.
	

Appropriate resuscitation equipment should be available in the room and a physician readily available during the period of drug administration.
		

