5.4 Dose Modification/Withholding

5.4.1 Dose Modifications of Pembrolizumab

No dose reductions of pembrolizumab are allowed.

Adverse events (both non-serious and serious) associated with pembrolizumab exposure may represent an immunologic etiology. These adverse events may occur shortly after the first dose or several months after the last dose of treatment.

Pembrolizumab must be withheld (not delayed) for drug-related toxicities and severe or life-threatening AEs as per Table 3 below. See Section 5.4 and Events of Clinical Interest Guidance Document for supportive care guidelines and management recommendations, including use of corticosteroids.

If criteria for resuming treatment are met, pembrolizumab treatment should resume at the next scheduled treatment timepoint (3 weeks later), or be permanently discontinued as per Table 3 below.

Although no dose delays for toxicity are allowed, an administrative delay within the allotted window of ± 7 days is allowed as per the Trial Flow Chart (Section 6.0). The next dose should be given when it is due according to the Trial Flow Chart with the goal of maintaining a consistent treatment schedule across all patients.

Dosing interruptions are permitted in the case of medical / surgical events or logistical reasons not related to study therapy (e.g., elective surgery, unrelated medical events, patient vacation, and/or holidays). Subjects should be placed back on study therapy within 3 weeks of the scheduled interruption, unless otherwise discussed with the study PI or co-PI. The reason for interruption should be documented in the patient's study record.

Table 3. Dose Modification and Toxicity Management Guidelines for Immune-related AEs Associated with Pembrolizumab

General instructions:				

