
 Corticosteroid taper should be initiated upon AE improving to Grade 1 or less and continue to taper over at least 4 weeks. For situations where pembrolizumab has been withheld, pembrolizumab can be resumed after AE has been reduced to Grade 1 or 0 and corticosteroid has been tapered. Pembrolizumab should be permanently discontinued if AE does not resolve within 12 weeks of last dose or corticosteroids cannot be reduced to ≤ 10 mg prednisone or equivalent per day within 12 weeks. For severe and life-threatening irAEs, IV corticosteroid should be initiated first followed by oral steroid. Other immunosuppressive treatment should be initiated if irAEs cannot be controlled by corticosteroids. 				
Immune-related AEs	Toxicity grade or conditions (CTCAEv4.0)	Action taken to pembrolizumab	irAE management with corticosteroid and/or other therapies	Monitor and follow-up
Pneumonitis	Grade 2	Withhold	
 Administer corticosteroids (initial dose of 1-2 mg/kg prednisone or equivalent) followed by taper 	
 Monitor participants for signs and symptoms of pneumonitis Evaluate participants with suspected pneumonitis with radiographic imaging and initiate corticosteroid treatment Add prophylactic antibiotics for opportunistic infections
	Grade 3 or 4, or recurrent Grade 2	Permanently discontinue		
Diarrhea / Colitis	Grade 2 or 3	Withhold	
 Administer corticosteroids (initial dose of 1-2 mg/kg prednisone or equivalent) followed by taper 	
 Monitor participants for signs and symptoms of enterocolitis (ie, diarrhea, abdominal pain, blood or mucus in stool with or without fever) and of bowel perforation (ie, peritoneal signs and ileus). Participants with \geq Grade 2 diarrhea suspecting colitis should consider GI consultation and performing endoscopy to rule out colitis. Participants with diarrhea/colitis should be advised to drink liberal quantities of clear fluids. If sufficient oral fluid intake is not feasible, fluid and electrolytes should be substituted via IV infusion.
	Grade 4	Permanently discontinue		

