All other immune-related AEs	Intolerable/persistent Grade 2	Withhold	
 Based on type and severity of AE administer corticosteroids 	
 Ensure adequate evaluation to confirm etiology and/or exclude other causes
	Grade 3	Withhold or discontinue based on the type of event. Events that require discontinuation include and not limited to: Guillain-Barre Syndrome, encephalitis		
	Grade 4 or recurrent Grade 3	Permanently discontinue		

1. Withhold or permanently discontinue pembrolizumab is at the discretion of the investigator or treating physician.

NOTE:
For participants with Grade 3 or 4 immune-related endocrinopathy where withhold of pembrolizumab is required, pembrolizumab may be resumed when AE resolves to \leq Grade 2 and is controlled with hormonal replacement therapy or achieved metabolic control (in case of T1DM).

Please refer to Section 5.6 Rescue Medications and Supportive Care for additional information on toxicity management.

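### Section 5.6.1 ties IV steroids for Grade 3-4 diarrhea/colitis to a longer persistence than oral steroids at Grade 2, and is inconsistent with Table 3, which sets no duration condition

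*SAP*

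**What the plan says.** Steroid treatment of diarrhea/colitis is described in two places in the SAP document.

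**Section 5.6.1 (Supportive Care Guidelines).** The diarrhea/colitis entry for Grade 2 reads "that persists greater than 3 days, administer oral corticosteroids". By contrast, the single entry covering both higher grades reads "that persists > 1 week, treat with intravenous steroids followed by high dose oral steroids". The section has no other steroid-starting instruction for Grade 3-4 colitis. It presents its measures as suggestions, which "are outlined below and in greater detail in the ECI guidance document", and applies them once the investigator has judged the event to be due to pembrolizumab.

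**Section 5.4.1, Table 3.** The diarrhea/colitis row says "Administer corticosteroids (initial dose of 1-2 mg/kg prednisone or equivalent) followed by taper". The general instructions at the top of the table add: "For severe and life-threatening irAEs, IV corticosteroid should be initiated first followed by oral steroid". Neither statement has a duration condition.

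**Cross-references.** The text introducing Table 3 says "See Section 5.4 and Events of Clinical Interest Guidance Document for supportive care guidelines and management recommendations, including use of corticosteroids". The note closing Table 3 says "Please refer to Section 5.6 Rescue Medications and Supportive Care for additional information on toxicity management". Section 5.6.1 points back with "Refer to Section 5.4 for dose modification". The ECI guidance document is named again in Section 11.4 of the Combined protocol and SAP, but it is not among the documents supplied.

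**The concern.** Two things look wrong. Within Section 5.6.1 the order is reversed: the more severe event has to last longer before its steroid instruction applies. Between the two sections, one text sets a duration condition and the other does not, for the same event and the same drug class.

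What is at stake is patient safety. Section 5.6.1 itself asks sites to watch these patients for bowel perforation. A site that takes its Grade 3-4 line literally could withhold IV steroids for more than a week in a patient whose severe colitis has already been attributed to pembrolizumab. A clinician who starts at Table 3 and follows its closing note arrives at exactly that line.

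**Working it through.** The plan has no figure to reproduce, so the check compares the texts, with a count and one subtraction.

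**1. Triggers side by side**

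| Grade | Section 5.6.1 | Table 3 |
|---|---|---|
| 2 | oral steroids after more than 3 days | steroids, no duration condition |
| 3 | IV, then high-dose oral, after more than 1 week | steroids, no duration condition; IV first if severe |
| 4 | as Grade 3 | IV first if life-threatening, no duration condition |

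Difference between the thresholds in Section 5.6.1: 7 - 3 = 4 days, longer at the higher grades. The two triggers start different treatments (oral against IV then high-dose oral), so this compares stated triggers. It does not measure delay to any steroid.

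In the extracted text the Grade 4 line of the Table 3 colitis row has no steroid wording of its own. The cell may be merged with the one above, as the pneumonitis row shows the same pattern, but that is an inference. For Grade 4 the comparison therefore rests on the general IV-first instruction alone.

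**2. Is a wait usual in Section 5.6.1?** Entries that prescribe steroids for a stated grade:

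- Grade 3-4: pneumonitis, colitis, hypophysitis, hyperthyroidism, hepatic, renal = 6, of which 1 has a wait (colitis).
- Grade 2: pneumonitis, colitis, hypophysitis, hepatic, renal = 5, of which 1 has a wait (colitis).

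Total 6 + 5 = 11 entries; 2 have a wait, both for diarrhea/colitis, and 9 have none. For Grade 3-4 pneumonitis the section asks for IV steroids at once.

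**3. Does finding the cause explain the week?** The section requires other causes to be sought and endoscopy to be considered from Grade 2 upward. Its treatment guidance, however, applies after attribution to pembrolizumab. Section 5.5.2 also permits systemic glucocorticoids when an immune cause is only suspected. A work-up period might explain some wait, but not a longer one at the higher grade.

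**4. Which text takes precedence?** Table 3 sends the reader to Section 5.6 for further toxicity management. Section 5.6.1 sends the reader back to Section 5.4 only for dose modification. The text before Table 3 names Section 5.4 and the ECI document for corticosteroid use. None of these says what to do where the two differ on steroid timing.

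**The case against.** The strongest reply is that the two texts can be read together: Table 3 supplies the dose and the order of routes, and Section 5.6.1 supplies the duration trigger. Table 3 never says when to start, and putting IV before oral fixes a sequence, not a speed. This part stands. A reader might infer that Table 3 orders prompt steroids and that Section 5.6.1 contradicts that order; the documents do not support so strong a reading. What remains is a conditional instruction against an unconditional one. Reading them together also leaves the reversed order of the triggers unexplained.

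A reader might also infer that Section 5.6.1 bars steroids in the first week. It does not. It is suggested care at the treating investigator's judgment, and earlier steroids are not forbidden.

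Third, it can be argued that the documents already rank Table 3 and the ECI document above Section 5.6.1, since the former are named for corticosteroid use and Section 5.6 is described as additional. That is a fair reading but not conclusive: the pointer to Section 5.4 sits inside Section 5.4 and may be a slip, and no sentence states precedence.

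Finally, other safeguards exist. Table 3 withholds pembrolizumab at Grade 2-3 and stops it at Grade 4. The inpatient-visit rules in Section 5.4 withhold both drugs for pembrolizumab-related non-skin events of Grade 2 or higher, isolated laboratory abnormalities excepted. Section 5.6.1 adds fluids and consideration of GI consultation and endoscopy. These reduce the risk but do not settle when steroids should start.

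**Conclusion.** The point holds as an internal inconsistency in safety guidance that should be corrected. In Section 5.6.1 the Grade 3-4 trigger exceeds the Grade 2 trigger by 4 days, only the two diarrhea/colitis entries of 11 carry any wait, and Table 3 sets none. Nothing in the supplied documents explains the longer trigger at the higher grade.

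The conclusion assumes that a site would take the Grade 3-4 line as its cue for starting steroids. That is the natural reading, because the section offers no other cue for those grades, but it remains an inference. How often a site would follow Section 5.6.1 rather than Table 3 cannot be estimated from the documents, so no number of affected patients is claimed. Whether the ECI guidance document already resolves the matter is unknown; even if it does, the two texts in the plan would still differ.

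No endpoint, sample size or analysis is affected. The Grade 2 difference (more than 3 days against no stated wait) is secondary.

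**What to change.** 1. In Section 5.6.1, delete the one-week persistence condition (the words before the comma in the passage quoted above) from the Grade 3-4 diarrhea/colitis entry. IV then oral steroids would then start once the event is judged pembrolizumab-related. Check the new wording against the ECI guidance document before issuing it.
2. Do not add a general statement that Table 3 overrides Section 5.6.1. It would displace other guidance: for Grade 3-4 hyperthyroidism Section 5.6.1 gives IV then oral corticosteroids, while Table 3 lists beta-blockers or thionamides. If a precedence line is wanted, restrict it to diarrhea/colitis.
3. Let the investigators choose one Grade 2 timing, either the 3-day trigger or none, and use it in both places.

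The cost is amendment wording and a clarification letter to sites, with no added patients, visits or procedures.
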